Our first primary aim is to test the 6-month efficacy of Tweet2Quit with biochemical verification of abstinence. We hypothesize that relative to usual care (n=240), Tweet2Quit-coed groups (n=480) will achieve significantly greater bioconfirmed sustained abstinence out to 6-months follow-up.

Aim 2

Our second primary aim is to test whether women do better in Tweet2Quit women-only versus coed groups. We hypothesize that women in Tweet2Quit will achieve significantly greater bioconfirmed 6-month abstinence in woman-only groups (n=240) vs. coed groups (n=240 women in those groups).

Secondary Aims will test the same hypotheses, however, based on 3-month (end of treatment) sustained and bioconfirmed abstinence rates and we will also test 7-day point prevalence abstinence at 1, 3, and 6 months.

Exploratory Aims will study the Tweet2Quit groups' social network structures with a focus on the identification of buddy pairs and social brokers, both via baseline theoretically-based measures and observed tweeting behaviors. In particular, we will test the following conceptual models positing how dyadic tie strength and betweenness centrality may serve as mechanisms of effects and promote smoking abstinence.

- *Better matched buddy pairs based on demographics → dyadic tie strength → dyad abstinence.*
- *Better social brokers based on self-monitoring → betweenness centrality → group tweets → group abstinence.*
- *These links will be stronger for women in women-only groups vs. women in coed groups of Tweet2Quit.*

3. List up to **ten relevant references/articles** to support the rationale for the research.

1. Joinson A, N. "Looking at", "looking up" or "keeping up with" people? Motives and use of facebook. Proceedings of the SIGCHI Conference on Human Factors in Computing Systems; April 5-10, 2008, 2008; Florence, Italy.
4. Baumann P. *140 Health care uses for twitter.* 2009; <https://vpn.nacs.uci.edu/+CSCO+0h756767633A2F2F637576796F6E687A6E61612E70627A++/140-health-care-uses-for-twitter/>. Accessed January 16, 2009.

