In Years 2-5, we will achieve Aim 1 and 2: to conduct a 3-arm cluster-randomized controlled trial of the 2nd generation *Tweet2Quit* Twitter-delivered group intervention. Both treatment (coed and women only) and control participants will receive a web-based quit plan referral, 8-weeks of nicotine patches and 8-weeks of nicotine gum/lozenges but the control groups will get this without Twitter support. Cohorts of 20-30 smokers that have passed the screening will be randomly assigned to treatment coed (with control) or treatment women only and then treatment participants will be grouped into demographically homophilous dyads or buddy pairs. Thus, both dyads and cohorts will be nested factors in the analyses.

Although UCI is collaborating with UCSF, Investigator [name] is not engaged in human-subjects research, given he is not interacting with participants, and he is not accessing identifiable data. UC Reliance #977 is *inactive*

Recruiting is a continuous ongoing activity and a new group is created once 20-30 applicants have completed the enrollment process. [name] will create a randomization table that will determine, e.g., every month, if the next cohort to be recruited will be coed or women-only, with 2/3rds of the cohorts being

coed and 1/3rd being women-only. A coed cohort of 30 smokers will have a minimum of 6 men (max. 10) and a maximum of 24 women (min. 20). Then, [name] will randomize 20 of these smokers to coed treatment and 10 smokers to coed control with the provisos that there be (a) a minimum of 4 men in coed tweet2quit (to ensure a critical mass), and (b) even numbers of men and even numbers of women in coed tweet2quit, i.e., 4, 6 or 8 not 3, 5 or 7 (for buddy pairing within gender). [name] will not see any identifiable subject data; he will only see anonymized subject numbers such as G01P01. If the treatment cohort to be recruited is women-only, then only women will be recruited. Any men that we also recruit will be waitlisted and placed in the next coed cohort. As treatment to control ratios of genders may not be equivalent, gender will be taken into account as a covariate during analysis.

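### The protocol gives two incompatible times for setting cohort type (coed or women-only); under the one its recruiting rules follow, staff would know the Aim 2 arm while enrolling women, and no concealment is described

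*Protocol*

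**What the plan says.** The Main Phase part of protocol Section 6.A gives two accounts of when a cohort becomes coed or women-only.

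- After screening: "Cohorts of 20-30 smokers that have passed the screening will be randomly assigned to treatment coed (with control) or treatment women only".
- Before recruitment: a randomisation table is to "determine, e.g., every month, if the next cohort to be recruited will be coed or women-only".

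The operating rules that follow fit the second account: "If the treatment cohort to be recruited is women-only, then only women will be recruited", and "Any men that we also recruit will be waitlisted and placed in the next coed cohort". The same paragraph also says: "Recruiting is a continuous ongoing activity and a new group is created once 20-30 applicants have completed the enrollment process".

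The one safeguard stated concerns the investigator who randomises: "he will only see anonymized subject numbers such as G01P01". The part of Section 6.A on collaborating campuses adds that this investigator has no contact with participants.

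Section 1 makes women-only versus coed groups, among women, the second primary aim, with 240 women on each side. The SAP describes these women as randomised and applies the Aim 1 type of model (logistic, generalised estimating equations, clustering by cohort) to women only. Beyond the terms of that model, the only covariates it may add are baseline predictors of attrition.

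**The concern.** Randomising clusters protects a comparison only if the people in each cluster were chosen without knowledge of its allocation. If cohort type is drawn first and the cohort is filled afterwards, whoever fills it can, knowingly or not, admit different women to the two types. Randomising the cohort labels does not undo that.

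There is some room for discretion. Advertising can be targeted by place, ethnicity and language (Section 4), and entry includes a webcam contact at which staff confirm the recruit's interest (Section 6.A, Enrollment Process). At stake is whether an Aim 2 difference in six-month abstinence can be attributed to group composition, or may partly reflect who was recruited into each type of group.

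**Working it through.** **Step 1. Design counts.**
- Coed groups: 480 / 20 = 24, matched by 240 / 10 = 24 control sets.
- Women-only groups: 240 / 20 = 12.
- 24 : 12 is the stated two-thirds to one-third split of cohorts.
- 480 + 240 + 240 = 960, plus the pilot cohort of 20, gives the 980 in Section 3.A.

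The figures are consistent, and Aim 2 rests on 24 + 12 = 36 cohort-level assignments. The documents state no effect size, power or intracluster correlation, so there is no power figure to reproduce.

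**Step 2. The two orders side by side.**

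| | Screen, then assign | Assign, then recruit |
|---|---|---|
| What is randomised | a cohort already screened | the label of a cohort not yet recruited |
| Can staff know the type while enrolling? | no, if the table is held back | yes: they must recruit only women and waitlist men |
| Could knowledge of the type affect who enters? | no | yes |

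The recruiting and waitlist rules can be carried out only under the right-hand column.

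**Step 3. What the stated safeguard covers.** Anonymised numbers protect the later split of an assembled coed cohort of 30 into 20 treatment and 10 control, which is the Aim 1 comparison. They do not hide cohort type from the people recruiting, which is the Aim 2 allocation.

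**Step 4. Whether the analysis would correct it.** In Aim 2 every cohort is wholly of one type. Allowing for clustering by cohort therefore changes the standard error but does not remove a difference in who was recruited. Covariates chosen because they predict attrition need not be those that differ by recruitment.

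**Step 5. Illustration of size.** Every input except 240 per arm is an assumption: a true six-month rate of 25% in both arms, and a standard-normal baseline predictor x with odds ratio (OR) 1.5 or 2.0 per SD, whose mean differs by 0.1 to 0.3 SD between arms.

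Model: logit p(x) = a + ln(OR) × x, with a set so that the average is 25% (a = −1.139 for OR 1.5, −1.210 for OR 2.0). The mean of x is then shifted and p is averaged again.

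With δ = p − 0.25 and SE = √[0.25 × 0.75/240 + p(1 − p)/240], the two-sided rejection rate is Φ(δ/SE − 1.96) + Φ(−δ/SE − 1.96).

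| Shift (SD) | OR 1.5: rate, rejection | OR 2.0: rate, rejection |
|---|---|---|
| 0.1 | 25.7%, 5.4% | 26.2%, 6.1% |
| 0.2 | 26.5%, 6.6% | 27.5%, 9.4% |
| 0.3 | 27.3%, 8.8% | 28.7%, 15.3% |

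Largest case: p = 0.2874, SE = 0.0404, δ/SE = 0.0374/0.0404 = 0.926, rejection 15.3%.

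With an assumed intracluster correlation of 0.02 and, for simplicity, 20 per group in both arms, the design effect is 1 + 19 × 0.02 = 1.38 and the effective size is 240/1.38 = 174 per arm. The range becomes 5.3 to 12.4%. The shift in the rate is unchanged; only the standard error grows.

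**The case against.** A reader might infer that Aim 2 allocation is in fact unconcealed, or that women for the two cohort types come from different advertisements or get different screening. The documents do not support either statement.

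- They do not say who sees the table or when. Staff knowledge is inferred from the recruiting and waitlist rules.
- One recruitment programme is described, with targeting by geography, ethnicity and language but not by sex or cohort type. Major changes in strategy need IRB approval (Section 4).
- Recruiting is called continuous, and men still arrive during women-only periods. That fits a single open stream in which sex only decides placement.
- Screening uses fixed criteria, e-mailed surveys and automated contact checks. Recruits are told only that the study may involve tweeting, and no passage offers women a choice of group.

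It is also fair to say that the illustration rests on chosen inputs. Its low end is negligible, and its high end needs the largest shift, the strongest predictor, the same direction across cohorts and no clustering.

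All of this stands, and it limits the point to a risk. It does not remove the contradiction. A uniform programme lowers the chance of differential selection, but the plan neither commits to keeping the stream the same during women-only periods nor says when the type is revealed.

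**Conclusion.** The concern holds as a contradiction that leaves a primary comparison open to selection after allocation. The two accounts of when cohort type is set are incompatible. If the second is followed as written, enrolling staff know the type while recruiting, no concealment from them is described, and the SAP has nothing aimed at the resulting imbalance.

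The size is unknown. On the assumed inputs, the Aim 2 false-positive rate would be about 5 to 15% instead of 5%, or about 5 to 12% with an assumed intracluster correlation of 0.02. These figures show what modest selection could do; they are not an estimate for this trial.

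The finding does not extend to Aim 1, where individuals are randomised within a coed cohort that is already enrolled. The plan should be changed, since the remedy is cheap, but nothing in the documents shows that Aim 2 is actually biased.

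**What to change.** **Protocol, Section 6.A.** Keep the screen-then-assign order and reword the recruiting rules to match.

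1. Run one recruitment stream at all times, with the same advertisements and screening for both sexes.
2. Keep the table with the off-site randomising investigator.
3. Reveal the next entry only when the screened pool could fill either cohort type with no further recruitment: 30 people, 20 to 24 women and 6 to 10 men, all through both screens. The two minimums alone are not enough. 20 + 6 = 26 cannot fill a coed cohort of 30, and the last 4 would be recruited after the reveal.
4. If the entry is women-only, take 20 women by a pre-set rule (at random, or in order of screening completion). Carry the remaining women and the men forward to the next pool.

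**SAP.** Compare women's baseline FTND and cigarettes per day by cohort type, and pre-specify both as covariates in the Aim 2 model. The screening survey already collects both.

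For any cohorts already formed under the assign-then-recruit order, say so. The baseline comparison and adjustment still help there, though they cannot remove unmeasured selection.

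**Cost.** An IRB wording change and more waiting. Some participants would start later, including women bound for women-only cohorts, who would wait until enough men had been screened. This matters because eligibility requires readiness to quit within 30 days. The second screening survey rechecks eligibility after a lapse but does not shorten it.

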All recruits will be e-mailed a survey that will screen for eligibility, and obtain contact information. The smoking-related screening criteria will include: must have smoked 100 cigarettes during their lifetime, must currently smoke 5 or more cigarettes a day, and must be in the preparation stage of quitting¹⁰⁰. Smoking five or more cigarettes per day is required due to use of nicotine patches (www.habitrol.com) . Additional screening criteria will be: ages 21-59 years, English speaking, have a mobile phone with an unlimited texting plan and internet access (via their mobile phone), use text messaging at least once a week, use social media regularly, have an active email account, live in the continental USA, and abide by the procedures of the study. To determine if a recruit is in the preparation stage of quitting, we will ask if they are ready to quit in the next 30 days.

Participants will be excluded if they have a medical condition that is contra-indicated for nicotine replacement therapy: pregnant, breast feeding, a recent heart attack, an irregular heartbeat, high blood pressure not controlled with medication, skin allergies to adhesive tape or serious skin problems, and/or taking a prescription medicine for depression or quitting smoking. They will also be disqualified if they use illicit drugs or if they use marijuana daily. They will be disqualified if someone else is already enrolled, or will be enrolled, in the study during the current grant period who lives in the same household or are immediate family to, or if they have failed the screening survey during the current grant period, or if they have previously been enrolled in the study in the current. Additionally, they will be disqualified if they participated in the prior grant period (HS# 2010-7990) as a member of the treatment group and did not tweet for more than a week (control group members can participate again). Research personnel will have access to list of previous participants (both those that passed and failed) to determine prior enrollment.

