In addition, participants will complete a contact form which will ask for their name, mobile phone, home and/or work phone if applicable, home mailing address (to get the nicotine patches and nicotine gum/lozenges), email address (to get survey links), Facebook URL or Social Media picture (to validate they have a social media account), identifying photo (to post on Tweet2Quit Twitter account if applicable and to verify identity for saliva testing), and username and password for our website (and Twitter if applicable). In addition, they will be asked to supply additional names, phone numbers, and email addresses of collaterals which will only be used as last resorts to contact the participants. If the participant fails to provide the required personal information, s/he will be disqualified. Also an automated program will send both an email and a text to each participant and require a response to ensure both accounts are valid. If a participant fails, their photo will not be downloaded from the survey database. Those that pass will have their photographs used to verify identity during webcam interviews (for saliva tests). If the

participant is enrolled into a Twitter group, their photo will be used for their profile picture. After the study concludes, all copies of the pictures will be destroyed.

The screening survey will also ask about age, gender, marital status, years of education, race/ethnicity, employment status, years smoking, cigarettes per day, number of prior quit attempts, age when they started smoking, type of cigarettes they used, the Fagerstrom Test for Nicotine Dependence (FTND), and the Thoughts about Abstinence Scale^{103,104}. It will also assess use of other tobacco and ENDS (electronic nicotine delivery) products. It will assess social media use, and self-monitoring and self-disclosure as personality traits. The screening survey will also explain the study requirements to participants (e.g., the study may involve tweeting and receiving text messages on mobile phones daily, will involve taking surveys, etc.) and it will confirm that the participant understands and agrees to these study requirements.

If participants fail the screen, they will be thanked and referred to NCI's Smokefree.gov Quit Guide. No more communication will occur and they will be blocked to prevent re-attempts at enrolling. Their data will be kept for screening analyses, but not used as part of the study results.

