participants who report that they are breastfeeding in our secondary survey will not be mailed nicotine patches, due to breastmilk contamination. Breastfeeding participants will be sent a 8-week supply of nicotine gum and a 8-week supply of nicotine lozenges instead, with corresponding instructions. Emails will also go out to notify all participants to follow the provided instructions. For those smoking 10+ cigarettes per day (as determined by the screening survey) they will be given 4 weeks of 21 mg patches, 2 weeks of 14 mg patches, and 2 weeks of 7 mg patches. If the participant smokes only 5-9 cigarettes per day (as determined by the screening survey) then they will receive 6 weeks of 14 mg patches and 2 weeks of 7 mg patches. All participants will receive 8 weeks of nicotine gum or lozenges to fight urges to smoke. No more than 12 pieces of gum or lozenges should be used a day. Participants smoking within 30 minutes of waking (determined by the screening survey) will receive 4mg and those that do not will receive 2 mg as the gum dosage. All participants requesting lozenges will receive the 1 mg dosage. We want to have as many smokers as possible in our recruitment pool, including the increasing number of light smokers, so we will include adults who smoke 5 or more cigarettes a day. We cannot go any lower than that due to the use of nicotine patches; nicotine replacement therapy is not recommended if a person smokes less than 5 cigarettes daily (www.habitrol.com).

We will provide free nicotine patches because clinical guidelines state that all smokers trying to quit should be offered pharmacotherapy unless contraindicated^{1,17}. The patches and gum/lozenges have few contraindications, so we expect few smokers to be excluded from our study for this reason. Further, the patches and gum/lozenges are available to most smokers because it is relatively low in cost (<\$2 per day) and often free to qualified smokers. Health insurance plans increasingly cover cessation pharmacotherapy including the nicotine patch. For example, Medi-Cal (the California Medicaid program) covers the cost of 8 weeks of nicotine patches for smokers in cessation programs such as the state's quitline. Nationally, Medicare Part D covers the costs of prescribed cessation medications, and nicotine patch can be prescribed. Also, LA County and other entities periodically have programs to give out free nicotine patches, e.g., at cooperating pharmacies.

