We anticipate minimal risks for participants. After completion of the study information sheet, all subject data will be encoded and password protected that only the research staff listed in this protocol will have access to. Participants will be assigned an ID which will prevent their name from being attached to all surveys. The website will be designed by a professional firm, WebAdvanced, experienced in developing secure environments, Twitter is a commonly used social network and participants are not being exposed to any deception or expected to behave any differently than they normally would while participating in a Twitter group.

Nicotine Replacement Therapy patches and gum/lozenges will be supplied to all participants; however a 21 CRF Part 312 is not required. NRT patches and gum/lozenges are sold over the counter and all participants will receive full instructions with the patches and gum/lozenges that fully explain usage and recommended dosing.

Additionally, all participants will be given the NRT patches and gum/lozenges, but are not required to use them to participate in the study.

Participants who report that they are breastfeeding in our secondary survey will not be mailed nicotine patches, due to breastmilk contamination. Breastfeeding participants will be sent a 8-week supply of nicotine gum and a 8-week supply of nicotine lozenges instead, with corresponding instructions.

B. Risks and Discomforts

1. Describe the **risks/potential discomforts** (e.g., emotional reaction from personal or sensitive information included in surveys, interviews, focus group, etc.; embarrassment or stigma; invasion of privacy) associated with each intervention or research procedure.

We anticipate minimal risks to participants.

All of the survey measures will be standard measures used in prior studies with participants who smoke. There have been no reports of distress or adverse effects from answering the surveys. A possible concern is that participants will be embarrassed if they do not quit smoking.

Possible Breach of Confidentiality

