The nicotine replacement therapy (NRT) that will be provided to participants as an incentive to participate and as part of the baseline intervention also poses potential risks, but they are minimal. NRT is available over the counter (www.habitrol.com), and is considered sufficiently safe for the general population, including those with high blood pressure monitored by medication or diabetes. Proper dosage and usage information will be included in each product shipment and on our study website. Some side effects that have been reported from NRT include application skin irritation, redness or itchiness, irritability, frustration, anger, craving, hunger, anxiety, difficulty concentrating, restlessness, insomnia, and mouth/throat irritation or soreness. All enrolled participants will receive NRT supplies appropriate to their smoking level and lasting for eight weeks (eight weeks for gum/lozenges), which is the period recommended by the manufacturer and approved by FDA. Step-down or tapered dosages will be used for the patches, as recommended by the manufacturer and approved by the FDA. The appropriate dosages of patches and gum/lozenges will be mailed to participants along with instructions. Participants who screen for any medical condition where NRT is counter-indicated will be excluded from the study. NRT use is not required to participate in the study, but is being provided because research indicates its potential in supporting smoking cessation efforts when used per instructions.

Alere iScreen OFD – Saliva Test Kit

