As previously mentioned, we anticipate minimal risks. The secure nature of the study website will ensure that participants and others cannot access the collected data, even their own data after survey completion. Each participant's records will be stored under a unique ID code, and no surveys or datasets will have names or personal identifiers on them; only the unique ID codes will be used. When the peer messages are downloaded into excel datasets, the personal identifiers (e.g., user names) will be replaced with the participants' unique ID codes. We will provide thorough set-up, instructions and guidelines to participants to send their Twitter messages as private, therefore ensuring the messages will not appear on the Twitter public timeline. Another protection is that participants will be free to stop participation at any time. If participants do not complete the follow-up surveys on line, they will be contacted by phone and asked to do the surveys over the phone, but they will not be pressured to do so. Participants will be eligible to receive small incentives for completing the surveys, but there will be no penalty for failing to complete the surveys.

The potential side effects of nicotine replacement therapy (NRT) will be clearly explained in the NRT packaging provided by the manufacturer. Participants who are counter-indicated for NRT will be excluded from the studies. Participants will be reminded of the medical conditions that are contraindicated for NRT use in their NRT shipments in case an excluded condition develops after initial consent (e.g., someone

becomes pregnant). Although all enrolled participants will receive NRT, using the NRT is not a condition of participation and if they experience discomfort they can discontinue the NRT without leaving the study.

Access to Data.

Data access will be limited to the study PIs [name] and [name] and the research staff, supervised by PI [name] and CR [name]. A file linking the participant ID with identifiable data will be stored separately in PI [name]'s locked office.

Data Protection.

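### The protocol excludes breastfeeding recruits as contraindicated for nicotine replacement, yet elsewhere keeps women who report breastfeeding and mails them nicotine gum and lozenges

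*Protocol*

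**What the plan says.** **Exclusion.** Section 6.A, Enrollment Process, lists the conditions that exclude a recruit as "contra-indicated for nicotine replacement therapy: pregnant, breast feeding, a recent heart attack" and several others. The same section says of those who fail the screen: "No more communication will occur and they will be blocked to prevent re-attempts at enrolling". Section 7.B repeats the exclusion in general terms, without naming breastfeeding. Under Nicotine Replacement Therapy it says "Participants who screen for any medical condition where NRT is counter-indicated will be excluded from the study", and under the steps to minimize risk it says "Participants who are counter-indicated for NRT will be excluded from the studies".

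**Retention and supply.** Section 7.A, Level of Risk, says "Participants who report that they are breastfeeding in our secondary survey will not be mailed nicotine patches, due to breastmilk contamination" and then "Breastfeeding participants will be sent a 8-week supply of nicotine gum and a 8-week supply of nicotine lozenges instead". Section 6.A, Standard Resources given to Participants, makes the same provision in nearly the same words.

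**What counts as nicotine replacement.** Section 7.A: "Nicotine Replacement Therapy patches and gum/lozenges will be supplied to all participants".

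**Shipment reminder.** Section 7.B, steps to minimize risk: "Participants will be reminded of the medical conditions that are contraindicated for NRT use in their NRT shipments in case an excluded condition develops". The sentence goes on to limit this to conditions arising after initial consent.

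**The concern.** Eligibility and product supply are operating instructions, and here they point in opposite directions for the same woman. Someone who reports breastfeeding in the *secondary survey* is excluded if staff apply the eligibility list. If they apply the supply text, she is enrolled and mailed two products of a class that the eligibility list treats as contraindicated for her.

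The inconsistency also reaches the risk assessment. Section 7.A places the supply provision in its justification for minimal-risk review, while Section 7.B offers exclusion of contraindicated people as a safeguard. Both statements stand in the same risk section without reference to each other.

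This is a matter of safety and eligibility. The wording covers all cohorts alike, so no bias in either primary comparison is alleged.

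**Working it through.** No formula applies; the check sets the texts side by side and makes two simple counts.

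**1. The instructions compared**

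| Place in the Protocol | Status of a woman who reports breastfeeding | Nicotine products mailed |
|---|---|---|
| Section 6.A, Enrollment Process | Excluded | 0 |
| Section 7.B, both general statements | Excluded, if breastfeeding is a contraindication as the Enrollment Process list says | 0 |
| Section 6.A, Standard Resources | Participant | 2 (8 weeks of gum + 8 weeks of lozenges) |
| Section 7.A, Level of Risk | Participant | 2 (8 weeks of gum + 8 weeks of lozenges) |

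**2. Which survey is meant?** The label *secondary survey* appears only in the two supply provisions and is not defined. The Main Phase Study Timeline lists five surveys: Screening Survey, Screening Survey 2, and those at 1, 3 and 6 months. Taking away the first screen and the three follow-ups leaves 5 − 1 − 3 = 1, namely Screening Survey 2. That is the most plausible referent, but it is an inference. The Enrollment Process text says the second screening survey exists to re-check eligibility when much time has passed.

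**3. Consequence under that reading.** A woman who reports breastfeeding at the first survey fails the screen and is blocked from applying again. A woman who reports it at the second, whose purpose is also eligibility, is kept in and supplied under the Standard Resources and Level of Risk text. Nothing in the protocol explains the difference.

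**4. Could the exclusion concern patches only?** The list removes the person from the study, not from one product, and names nicotine replacement therapy as a class. Section 7.A puts gum and lozenges in that class. The Standard Resources text also links the number of exclusions it expects to contraindications of patches and gum/lozenges together.

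**5. The reminder.** Its content is not in the documents. If it follows the Enrollment Process list, a shipment adapted because a woman is breastfeeding would also tell her that breastfeeding is contraindicated. This point is conditional, and the contradiction does not depend on it.

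**6. Number affected.** The documents give no count or rate of breastfeeding at either survey, so no number can be derived.

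**The case against.** The strongest defence is a staged reading: the first survey excludes, and the supply provision covers only women who first report breastfeeding later. The timing gives it some support. The study information sheet is part of the first screening survey, and Section 7.B answers conditions arising after consent with a reminder, not removal. It would be a workable rule, but the protocol never states it. It also sits badly with a second survey meant to confirm eligibility, and with Section 7.B's unqualified exclusion of anyone who screens positive for a contraindication.

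A second defence is that the list is partly about patches. It includes adhesive allergy and skin problems, and the five-cigarette minimum is justified by patch use. That is true of those items, but it does not turn exclusion from the study into exclusion from one product.

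Third, the supply provision is deliberate. It is written as an exception to the general mailing rule, gives its own reason, promises matching instructions with the products, and appears openly in the risk section. All of this stands, and it makes an exclusion list that was never updated a likely cause. But an exception to the mailing rule is not an exception to the eligibility list.

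Finally, nicotine replacement is optional and can be stopped without leaving the study (Section 6.A, Standard Resources; Section 7.B). That lessens the exposure but does not settle who is eligible or what is mailed.

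**Conclusion.** The concern holds, and the text must be corrected. For a woman who reports breastfeeding in the *secondary survey*, the protocol gives incompatible instructions: exclusion with no nicotine supply, or participation with two 8-week supplies. No exception or precedence resolves them.

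Confidence in the textual conflict is high. The account of different treatment at the two surveys rests on the inference that the *secondary survey* is Screening Survey 2; the conflict between the eligibility list and the supply provision does not. The number of women affected is unknown, and no effect on the Aim 1 or Aim 2 estimates is claimed. No view is taken on which clinical rule is right.

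**What to change.** - Have the investigators and the IRB choose one rule for a woman who reports breastfeeding, stated separately for each screening survey.
- Write that rule consistently into Section 6.A (Enrollment Process and Standard Resources), Section 7.A and both statements in Section 7.B, and into the logic of both screening surveys.
- Define the *secondary survey*, or replace the label with the name used in the study timeline.
- Check that the contraindication reminder in the shipments agrees with the rule.
- If enrolment has closed, record which rule was applied in practice and to how many women.

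The cost is small: amendment wording, matching survey logic and a check of the reminder, or a documented note if enrolment is over.
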